1.3 History of Amendments

Changes in paragraphs:

1. Section 4: Hepatitis B and C Screening.
2. Section 5.2: Exclusion Criteria # 14.
3. Table 3: Criteria for Dose Modification in Case of Suspected RAD001 Toxicity.
4. Table 5: Action to be taken based on Screening Hepatitis B Results.
5. Table 6: Guidelines for the management of Hepatitis B reactivation.
6. Table 9: Visits Evaluation Schedule:

CT scan or MRI of chest, abdomen, and pelvis- If the CT scan was performed during the screening (in the range of 35 days) it does not need to be performed again at baseline.

Pulmonary Function Test- will be performed at screening per investigator discretion.

7. Section 7.5.1: Radiological Assessment of Tumor(s).
8. Section 7.6.5.8: Chest X-Ray/Chest Computed Scans/Pulmonary Function Tests.
9. Section 10.5.1.3: Overall Survival Definition.
10. Table 10: Updated country, # of patients, and #of sites.
11. Section 10.1: Population for Analysis.
12. Section 10.5.1.3: Overall Survival.

2 Study Rationale

Current standard therapies (chemotherapies and cytokine-based therapies) have produced few and short-lived tumor responses, and are associated with severe toxicities. It is clear that novel therapies are needed for patients with advanced RCC, including those with metastatic disease and those whose tumors are not amenable to surgical resection. Although sunitinib and temsirolimus have improved PFS or OS, in comparison with IFN, and the addition of bevacizumab to IFN has led to improved results in comparison with single-agent IFN, in some countries IFN remains the only available treatment option for patients with advanced RCC.

A smaller sub-group analysis of patients with “other” subgroup category (non-clear and indeterminate histologies), the HR analysis for OS suggested an advantage for temsirolimus (an iv mTOR inhibitor) over IFN ([Dutcher, et al., 2007](#)).

The oral formulation of RAD001 presents an improvement in the delivery of anticancer therapy, with direct impact on the patient and the health care delivery system. RAD001 is generally well tolerated at 10 mg daily doses (see [Table 1](#)).

RAD001 has been studied extensively in solid organ transplantation (renal and cardiac) where over 1000 patients have received RAD001 for ≥ 3 years, with the drug being given as a constituent of an immunosuppressive regimen, which included cyclosporine (a CYP3A4 inhibitor) and glucocorticoids.

Pharmacodynamic modeling indicates that downstream effectors of mTOR are completely suppressed by RAD001 at the 10 mg/day. Preliminary results of MPD studies in biopsied tumor tissue suggest a dose-related decrease in p-4E-BP1 and increase in p-AKT expression, with maximal effect at 10 mg daily.

The proposed dose and schedule (10 mg/day) is based on various Phase 1 and Phase 2 studies (monotherapy and combination therapy) in advanced cancers, including RCC. This dose and schedule also showed significant efficacy in a large placebo-controlled Phase 3 study in patients with MRCC who previously progressed on anti-VEGF targeted therapy.

The purpose of this open-label, multi-center, Phase 2 study is to demonstrate the safety and efficacy of RAD001 10 mg po daily dose, as monotherapy, in patients with metastatic carcinoma of the kidney with clear cell and non-clear cell histology and all MSKCC prognosis, who have not received prior systemic treatment other than cytokine therapy.

3 Objectives

3.1 Primary Objective

The primary objective of the study is to evaluate the PFS rate over time.

3.1.1 Endpoint for Primary Objective

The primary efficacy endpoint is PFS (i.e., remaining free from disease progression and death).

3.2 Secondary Objectives

The secondary objectives of the study are:

1. To evaluate the disease control rate (stable disease [SD] + partial response [PR] + complete response [CR]) (SD + PR + CR);
2. To evaluate the objective response rate (ORR; where ORR = CR + PR);
3. To evaluate duration of response;
4. To evaluate OS;
5. To describe the safety profile of RAD001.

3.2.1 Endpoints for Secondary Objectives

Secondary endpoints include:

- Disease control rate (SD + PR + CR);
- ORR;

- Response duration;
- OS;
- Safety will be assessed using CTCAE version 3.0. Safety parameters include AEs, laboratory , and other safety parameters as appropriate.

4 Study Design

This is an open-label, multi-center, single arm Phase 2 study to evaluate the safety and efficacy of RAD001 as monotherapy in patients with any MSKCC prognosis metastatic recurrent and/or unresectable clear cell or non-clear cell carcinoma of the kidney. Patients who have received prior cytokine therapy are permitted to participate in the study.

Tumor assessments will be performed at 8 weeks to evaluate for inadequate response (progressive disease [PD]). The visit at which PD is documented will be deemed the End-of-Treatment Visit.

In the absence of PD, assessments will continue every 12 weeks (± 1 week) until the start of new anticancer therapy and at the End-of-Treatment Visit (within 1 week of stopping treatment) or until death. A PR or CR warrants confirmation no sooner than 4 weeks.

Follow-up phase: All patients will have a follow-up visit scheduled 28 days after the End-of-Treatment Visit to follow for AEs and SAEs that may have occurred after discontinuation from the study. Any patient who is discontinued from study treatment for any reason will continue to have tumor assessments every 12 weeks (± 1 week) until the patient is switched to another anticancer therapy or until death. The investigator or his/her designee will continue collecting information on the initiation of additional anticancer therapies until the date of data cutoff for the final analysis (see [Section 10.6](#)). All new anticancer therapies after the last dose of study treatment will be recorded on the appropriate case report form (CRF) page.

Study drug refers to RAD001. All patients who meet the study entry criteria will receive RAD001. It is anticipated that approximately 110 patients will be enrolled in the study.

Hepatitis B and C Screening

In cancer patients with hepatitis B, whether carriers or in chronic state, use of antivirals during anticancer therapy has been shown to reduce the risk of HBV reactivation and associated HBV morbidity and mortality ([Loomba et al. 2008](#); [Sorrell et al. 2009](#)).

During the screening period, ALL patients must be screened for HBV and HCV (current or past history of infection). Careful medical history must be taken for all patients to look for risk factors (family history of HBV and HCV, intravenous drug abuse, unprotected sex, dialysis, blood transfusions, etc), and any past or present HBV symptoms (e.g., jaundice, dark urine, light-colored stools, right upper quadrant pain). All patients will be tested for HBV-DNA and serological markers, and HCV viral load by quantitative RNA-PCR. It is highly recommended that patients at risk of HBV reactivation are treated prophylactically with antivirals for 1-2 weeks prior to receiving study drug and for at least 4 weeks after last dose of study drug. The management guidelines, in [Section 6.1.4.4](#), are provided according to the results of the screening assessment of viral load and serological markers for HBV and HCV.

5 Population

Adult patients who have metastatic recurrent and/or unresectable renal cell carcinoma are eligible for enrollment in this study. Previous cytokine therapy is permitted. Patients must have histological or cytological confirmation of clear cell or non-clear cell renal carcinoma or a component of these histologies. The treating oncologist is advised to consider biopsy of lesions to establish the diagnosis of MRCC if there is substantial clinical ambiguity regarding the nature or source of primary disease.

Inclusion/exclusion criteria

The investigator or his/her designee must ensure that all patients who meet the following inclusion and exclusion criteria are offered enrollment in the study. No additional exclusions can be applied by the investigator, in order that the study population will be representative of all eligible patients.

Patients must have screening evaluations performed to ensure potential patients being considered by the investigator meet all inclusion and exclusion criteria. Results of all screening evaluations, which assure that all inclusion and exclusion criteria have been satisfied, must be reviewed by the Principal Investigator or his/her designee, prior to enrollment of that patient into the study. Local laboratory results will be used to determine patient eligibility for the study.

All study patients must be thoroughly informed about all aspects of the study, including the study visit schedule, required evaluations, and all regulatory requirements for informed consent. The written informed consent must be obtained prior to the performance of any screening evaluations. If the patient is unable to read, an impartial witness should be present during the entire informed consent discussion. The following criteria apply to all patients enrolled into the study, unless otherwise specified.

5.1 Inclusion Criteria

Patients may be entered in the study only if they meet all of the following criteria:

1. Age \geq 18 years old;
2. Patients with advanced renal cell carcinoma with confirmed clear or non-clear cell histology, with or without nephrectomy, and with any MSKCC prognosis;
3. Prior cytokine therapy is permitted;
4. Patients with at least one measurable lesion at baseline as per the RECIST criteria. If skin lesions are reported as target lesions, they must be documented (at baseline and at every physical exam) using color photography and a measuring device (such as a caliper) in clear focus to allow the size of the lesion(s) to be determined from the photograph;

5. Life expectancy ≥ 3 months. Life expectancy should be judged in relation to other determining patient eligibility factors such as laboratory results, Performance Status, etc.;
6. Patients with a Karnofsky Performance Status $\geq 70\%$;
7. Adequate bone marrow function as shown by: absolute neutrophil count (ANC) $\geq 1.5 \times 10^9/L$, platelets $\geq 100 \times 10^9/L$, hemoglobin (Hb) > 9 g/dL;
8. Adequate liver function: serum bilirubin ≤ 1.5 x upper limit of normal (ULN), alanine transaminase (ALT) and aspartate transaminase (AST) ≤ 2.5 x ULN. Patients with known liver metastases: AST and ALT ≤ 5 x ULN;
9. Adequate renal function: serum creatinine ≤ 1.5 x ULN;
10. Females of childbearing potential must have had a negative serum or urine pregnancy test 7 days prior to the administration of the study treatment start;
11. Patients who give a written informed consent obtained according to local guidelines.

5.2 Exclusion Criteria

Patients may not be entered into the study if they meet any of the following criteria:

1. Patients within 2 weeks post-minor surgery (e.g., herniorrhaphy), 4 weeks post-major surgery (e.g., intra-thoracic, intra-abdominal, or intra-pelvic) to avoid wound healing complications. Percutaneous biopsies require no waiting time prior to study entry;
2. Patients with a recent history of hemoptysis, ≥ 0.5 teaspoon of red blood;
3. Patients who have received prior systemic treatment for their metastatic RCC other than cytokine therapy;
4. Patients who received prior therapy with a VEGF pathway inhibitor, such as sunitinib, sorafenib, and bevacizumab;
5. Patients who have previously received mTOR inhibitors (sirolimus, temsirolimus, everolimus, deferolimus);
6. History or clinical evidence of central nervous system (CNS) metastases. Note: Subjects who have previously-treated CNS metastases (surgery \pm radiotherapy, radiosurgery, or gamma knife) and meet all 3 of the following criteria are eligible:
 - Are asymptomatic;
 - Have had no evidence of active CNS metastases for ≥ 6 months prior to enrollment and;
 - Have no requirement for steroids or enzyme-inducing anticonvulsants (EIAC);
7. Clinically significant gastrointestinal abnormalities including, but not limited to:
 - Malabsorption syndrome;
 - Major resection of the stomach or small bowel that could affect the absorption of study drug;

- Active peptic ulcer disease;
 - Inflammatory bowel disease;
 - Ulcerative colitis, or other gastrointestinal conditions with increased risk of perforation;
 - History of abdominal fistula, gastrointestinal perforation, or intra abdominal abscess within 28 days prior to beginning of study treatment;
8. Patients receiving chronic systemic treatment with corticosteroids or another immunosuppressive agent. Inhaled and topical steroids are acceptable;
 9. Patients with a known history of human immunodeficiency virus seropositivity;
 10. Patients with autoimmune hepatitis;
 11. Patients with an active, bleeding diathesis. Patients may use coumadin or heparin preparations;
 12. Patients who have any severe and/or uncontrolled medical conditions or other conditions that could affect their participation in the study such as:
 - unstable angina pectoris, symptomatic congestive heart failure, myocardial infarction ≤ 6 months prior to first study treatment, serious uncontrolled cardiac arrhythmia;
 - uncontrolled diabetes as defined by fasting serum glucose $> 1.5 \times$ ULN;
 - any active (acute or chronic) or uncontrolled infection/disorders that impair the ability to evaluate the patient or for the patient to complete the study;
 - non-malignant medical illnesses that are uncontrolled or whose control may be jeopardized by the study treatment, such as severe hypertension that is not controlled with medical management and thyroid abnormalities whose thyroid function cannot be maintained in the normal range by medication;
 - liver disease such as cirrhosis, decompensated liver disease, chronic active hepatitis, or chronic persistent hepatitis;
 - fatal or life-threatening autoimmune and ischemic disorders;
 13. Patients who have a history of another primary malignancy ≤ 3 years, with the exception of non-melanoma skin cancer and carcinoma in situ of uterine;
 14. Female patients who are pregnant or breastfeeding, or adults of reproductive potential who are not using effective birth control methods. If barrier contraceptives are being used, these must be continued throughout the study by both sexes. Oral contraceptives are not acceptable as the only contraception method. However they can be used in combination with other methods such as barrier contraceptives;
 15. Patients who are using other investigational agents or who had received investigational drugs ≤ 4 weeks prior to study treatment start;
 16. Patients unwilling or unable to comply with the protocol.

6 Treatment

6.1 Investigational and Control Drugs

6.1.1 Study Drug

The investigational drug used in this study is RAD001. The study drug will be self-administered (by the patients themselves). The investigator will instruct the patient to take the study drug exactly as specified in the protocol.

Patients will be instructed to take two 5 mg RAD001 tablets (one tablet after another) orally, with a glass of water at the same time each day, in a fasting state or with a light fat-free meal.

If vomiting occurs, no attempt should be made to replace the vomited dose. Any dietary habits around the time of RAD001 intake should be as consistent as possible throughout the study.

RAD001 will be taken daily from Visit 2 (Day 1) until disease progression, unacceptable toxicity, or death or discontinuation from the study for any other reason.

6.1.2 Known Undesirable Effects of RAD001

Adverse events most frequently observed with RAD001 are rash, stomatitis/oral mucositis, fatigue, headache, anorexia, nausea, vomiting, diarrhea, ocular toxicity, and infections. Non-infectious pneumonitis has also been observed as indicated in [Section 1.2.3.3](#).

Overall, the most frequently observed laboratory abnormalities include neutropenia, thrombocytopenia, hypercholesterolemia, and/or hypertriglyceridemia. The majority of these AEs have been of mild to moderate severity (CTC grade 1 to grade 2). Refer to [Table 3](#) for management of laboratory abnormalities.

6.1.3 RAD001 Dose Level Modification/Interruption Guidelines in Case of Suspected Toxicity

Dose adjustments are permitted in those patients who are unable to tolerate the protocol-specified dosing schedule. If administration of RAD001 must be interrupted because of unacceptable toxicity, drug dosing will be interrupted or modified according to rules described in [Table 2](#), [Table 3](#), and [Table 4](#).

If the toxicity is tolerable to the patient, the initial dose should be maintained. If the toxicity is intolerable to the patient, RAD001 treatment is to be interrupted until recovery to grade ≤ 1 , then reintroduced at the initial dose or a lower dose level, depending on toxicity type and grade (see [Table 3](#)). All interruptions or dose modifications must be recorded on the Dosage Administration Record CRF.

Table 2 RAD001 Dose Level Modification Guidelines

Dose Level	Dose Schedule
0	10 mg daily
1	5 mg daily
2	5 mg every other day

Table 3 provides the procedure to be followed for dose modification and re-initiation of RAD001 in the event of toxicities suspected to be related to the study drug.

Table 3 Criteria for Dose Modification in Case of Suspected RAD001 Toxicity

Toxicity	Actions
Non-hematological toxicity	
Grade 1	No dose modification.
Grade 2 (except pneumonitis):	If the toxicity is tolerable to the patient, maintain the same dose. If toxicity is intolerable to the patient, interrupt RAD001 until recovery to grade ≤ 1 , then re-introduce RAD001 at the same dose. If the event returns to grade 2, interrupt RAD001 until recovery to grade ≤ 1 , then re-introduce at the lower dose level.
Grade 3 (except hyperlipidemia):	Interrupt RAD001 until recovery to grade ≤ 1 , then re-introduce at the lower dose level. For pneumonitis, consider the use of a short course of corticosteroids.
Grade 3 hyperlipidemia (hypercholesterolemia and/or hypertriglyceridemia):	Should be managed using standard medical therapies.
Grade 4:	Discontinue RAD001.
Reactivation of HBV or HCV	Please refer to Tables 6 and 7 .
Hematological toxicity	
Grade 1	No dose modification.
Grade 2 thrombocytopenia (platelets $<75 \times 10^9/L$, $\geq 50 \times 10^9/L$):	Interrupt RAD001 until recovery to grade ≤ 1 (platelets $\geq 75 \times 10^9/L$), then re-introduce RAD001 at the initial dose. If thrombocytopenia returns to grade 2, interrupt RAD001 until recovery to grade ≤ 1 , then re-introduce at the lower dose level.
Grade 3 thrombocytopenia (platelets $<50 \times 10^9/L$, $\geq 25 \times 10^9/L$):	Interrupt RAD001 until recovery to grade ≤ 1 (platelets $\geq 75 \times 10^9/L$), then resume RAD001 at 1 dose level lower. If grade 3 thrombocytopenia recurs, discontinue RAD001.
Grade 4 thrombocytopenia (platelets $<25 \times 10^9/L$):	Discontinue RAD001.
Grade 3 neutropenia (neutrophils $<1 \times 10^9/L$, $\geq 0.5 \times 10^9/L$):	Interrupt RAD001 until recovery to grade ≤ 1 (neutrophils $\geq 1.5 \times 10^9/L$), then resume RAD001 at initial dose. If absolute neutrophil count (ANC) returns to grade 3, hold RAD001 until recovery to grade 1 (ANC $\geq 0.5 \times 10^9/L$), then resume RAD001 at the lower dose level. Discontinue patient from study therapy for a third episode of grade 3 neutropenia.
Grade 4 neutropenia (neutrophils $<0.5 \times 10^9/L$):	Interrupt RAD001 until recovery to grade ≤ 1 (neutrophils $\geq 1.5 \times 10^9/L$), then resume RAD001 at the lower dose level. If grade 3 or grade 4 neutropenia occurs despite this dose reduction, discontinue RAD001.
Grade 3 febrile neutropenia (not life-threatening):	Interrupt RAD001 until resolution of fever and neutropenia to grade ≤ 1 . Hold further RAD001 until the ANC $\geq 1500/mm^3$ and fever has resolved. Resume RAD001 at the lower dose level. If febrile neutropenia recurs, discontinue RAD001.
Grade 4 febrile neutropenia (life-threatening):	Discontinue RAD001.
Any hematological or non-hematological toxicity	Discontinue RAD001.

requiring interruption for ≥ 3 weeks:

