1.2.3.3 Phase 1 Oncology Studies

Data are available from Phase 1 clinical studies of RAD001 given as a single agent to 147 patients with advanced solid tumors. Such studies included various doses and schedules (weekly dosing, range 5 mg to 70 mg and daily dosing 5 mg to 10 mg). Approximately 46%

of patients reported rash or erythema and 40% of the patients presented with stomatitis/mucositis. The most frequent AEs suspected to be drug-related observed in 3 studies using RAD001 as a single-agent are listed in Table 1.

Table 1 Adverse Events Suspected to be Drug-Related in ≥10% of Patients with Advanced Cancers Reported in Phase 1 RAD001 Monotherapy Studies (C2101, C2102, and C2107)

	Weekly			Daily		Total n=147
	5-30 mg n=30	50 mg n=18	70 mg n=38	5 mg n=16	10 mg n=45	
Number of Patients with Adverse Event						
Any event	23 (1)	17 (2)	38 (10)	14 (1)	43 (14)	135 (28)
By event						
Rash	5	8	18	10	27 (1)	68 (1)
Stomatitis/mucositis	6	8 (2)	16 (2)	6 (1)	23 (3)	59 (8)
Fatigue	8	7 (1)	14 (1)	1	17 (1)	47 (3)
Nausea	5	4	8	2	18 (1)	37 (1)
Anorexia	1	6	10	3	15	35
Diarrhea	1	7	7	-	9	24
Vomiting	4	5	5	-	10	24
Headache	7	4	6	6	4	20
Pruritis	2	1	6	3	4	16
Infections	1	3	2	1	4 (1)	14 (1)
Constipation	-	1	2	2	9	14

[figure not shown]
The number of patients (by dose level and dose schedule) who have reported grade ≥3 toxicities is given in brackets. There were no RAD001 suspected grade 4 adverse events.

Infections noted as drug-related included:

Herpes simplex	4 patients (1 at 50 mg/week; 1 at 5 mg/day; 2 at 10 mg/day)
Oral candidiasis	5 patients (1 at 20 mg/week; 1 at 50 mg/week; 2 at 70 mg/week; 1 at 10 mg/day)
Pneumonia (grade 3)	1 patient (10 mg/day)
Rhinitis	2 patients (50 mg/week)
Upper respiratory tract infection	1 patient (50 mg/week)
Urinary tract infection	1 patient (50 mg/week)

Reduced blood cell counts at the initiation of treatment are frequent, but remain mostly within the normal range or limited to grade 1, although a grade 3 neutropenia was a dose-limiting toxicity (DLT) in one patient, as was a grade 3 thrombocytopenia in a patient receiving RAD001 with letrozole, where pharmacodynamic interaction is unlikely. This suggests that some patients may be particularly sensitive to the myelosuppressive effect of RAD001, making it necessary to carefully monitor blood cell counts at the initiation of treatment.

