6.1.4.2 Management of Hyperlipidemia and Hyperglycemia

Treatment of hyperlipidemia should take into account the pre-treatment status and dietary habits of the patient. Blood tests to monitor hyperlipidemia must be taken in the fasting state.

Grade 2 or higher hypercholesterolemia (>300 mg/dL or 7.75 mmol/L) or grade 2 or higher hypertriglyceridemia ($>2.5 \times$ ULN) should be treated with a statin or appropriate lipid-lowering medication, in addition to diet. Patients should be monitored clinically and through

serum biochemistry for the development of rhabdomyolysis and other AEs as required in the product label/data sheets for HMG-CoA reductase inhibitors.

Note: Concomitant therapy with fibrates and an HMG-CoA reductase inhibitor is associated with an increased risk of a rare, but serious, skeletal muscle toxicity manifested by rhabdomyolysis, markedly elevated creatine phosphokinase levels and myoglobinuria, acute renal failure, and sometimes death. The risk versus benefit of using this therapy should be determined for individual patients based on their risk of cardiovascular complications of hyperlipidemia.

Grade 3 hyperglycemia has been observed in patients receiving RAD001 therapy. In many cases in Study RAD001C2222, the affected patients had an abnormal fasting glucose at baseline. Based on this finding, it is recommended that optimal glucose control be achieved before starting a patient on RAD001. Study patients should have their glucose levels monitored during RAD001 therapy.

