6.1.4.3 Management of Non-Infectious Pneumonitis

Both asymptomatic radiological changes (grade 1) and symptomatic non-infectious pneumonitis (grade 2 = not interfering with activities of daily living or grade 3 = interfering with activities of daily living and oxygen indicated) have been noted in patients receiving RAD001 therapy. Non-infectious pneumonitis has been associated with RAD001 and other mTOR inhibitors (Atkins, et al., 2004).

In order to monitor for asymptomatic (grade 1) non-infectious pneumonitis, a chest x-ray or CT scan is required in addition to the 3-monthly CT or magnetic resonance imaging (MRI) tumor examinations.

Additional chest x-rays or CT scans may be performed, when clinically necessary. If non-infectious pneumonitis develops, a consultation with a pulmonologist should be considered. If the patient develops grade 3 pneumonitis, treatment with RAD001 should be interrupted and the patient should be treated as medically indicated (short course corticosteroids, oxygen, etc.).

Chest x-ray/chest CT scans obtained during the study should be readily accessible at the site and must be kept with the patient's source documents.

Dose modification instructions and Management of non-infectious pneumonitis suspected to be associated with RAD001 and are provided in [Table 3](#) and [Table 4](#).

Table 4 Management of Non-Infectious Pneumonitis

Worst Grade Pneumonitis	Required Investigations	Management of Pneumonitis	RAD001 Dose Adjustment
Grade 1	CT scans with lung windows. Repeat every 3 cycles until return to within normal limits.	No specific therapy is required.	Administer 100% of RAD001 dose.
Grade 2	CT scans with lung windows and required pulmonary function testing includes: spirometry, DLCO, and room air O ₂ saturation at rest. Repeat each subsequent cycle until return to baseline. Consider a bronchoscopy. ^a	Symptomatic only. Prescribe corticosteroids if cough is troublesome.	Reduce RAD001 dose until recovery to ≤ grade 1. RAD001 may also be interrupted if symptoms are troublesome. Patients should be withdrawn from the study if they fail to recover to ≤ grade 1 within 3 weeks.

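### Section 6.1.3 keeps the dose for any tolerable toxicity without a grade limit, while Table 3 requires action at non-hematological grade 3 (except hyperlipidemia) and grade 4 whether or not the event is tolerated (low severity)

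*Protocol*

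**What the plan says.** Section 6.1.3 opens by allowing dose adjustment for patients who cannot tolerate the schedule. It sends the reader to Tables 2, 3 and 4 when dosing has to be interrupted for unacceptable toxicity. Two general sentences follow. The first is "If the toxicity is tolerable to the patient, the initial dose should be maintained". The second says that an intolerable toxicity leads to interruption until grade 1 or below and then a restart at the initial or a lower dose. Type and grade enter only there, in choosing the restart dose.

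Table 3 is then introduced: "Table 3 provides the procedure to be followed for dose modification and re-initiation of RAD001". Its non-hematological grade 2 row (pneumonitis excepted) contains a tolerability test: "If the toxicity is tolerable to the patient, maintain the same dose". Its grade 3 row (hyperlipidemia excepted) contains none. It interrupts until recovery to grade 1 or below, "then re-introduce at the lower dose level. For pneumonitis, consider the use of a short course of corticosteroids". Grade 4 means discontinuation. Grade 3 hyperlipidemia is managed medically.

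Three other places lean on the tables. Section 6.1.2 refers the reader to Table 3 "for management of laboratory abnormalities". Section 6.1.4.3 says "If the patient develops grade 3 pneumonitis, treatment with RAD001 should be interrupted". SAP 3.2 names Tables 2 to 4 as the source of the interruption and modification rules.

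**The concern.** For a tolerated grade 3 non-hematological event the two parts of 6.1.3 give opposite instructions: stay on the initial dose, or interrupt and come back lower. The sentence that keeps the dose comes first, is written as a general rule, and has no exception.

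At stake is consistent application of a safety dosing rule across the 25 planned sites. Section 12 permits no authorized deviations, so a site that followed either instruction could be said to have departed from the other. SAP 8.1 also counts patients with a treatment-emergent event leading to modification of study medication, and uneven practice would blur that descriptive count.

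**Working it through.** **Step 1: set the rules side by side** (Section 6.1.3 and Tables 2 to 4, for an event the patient tolerates)

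| Event | 6.1.3 sentence | Table |
|---|---|---|
| Non-hematological grade 2, not pneumonitis | keep dose | keep dose: agrees |
| Non-hematological grade 3, not hyperlipidemia | keep 10 mg daily | interrupt, restart at 5 mg daily (level 1): **conflicts** |
| Grade 3 hyperlipidemia | keep dose | medical management, no dose action listed: no conflict |
| Non-hematological grade 4 | keep dose | discontinue: **conflicts** |
| Pneumonitis grade 2 (Table 4) | keep dose | reduce: conflicts literally |
| Thrombocytopenia grades 2 to 4, neutropenia grades 3 and 4 | keep dose | interrupt or discontinue by grade: conflicts literally |

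**Step 2: look for a ranking clause.** The lead-in to Table 3 favors the table but does not override the earlier sentence. Section 6.6.3 points back to 6.1.3 as a whole, so it settles nothing. Section 6.1.2 covers laboratory abnormalities, and 6.1.4.3 with Table 4 covers pneumonitis. What remains with no specific pointer is mainly a tolerated grade 3 non-hematological event that is neither pneumonitis nor a laboratory finding. Grade 4 is a remote case on the available data: in the phase 1 monotherapy studies, "There were no RAD001 suspected grade 4 adverse events".

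**Step 3: size, from Table 1 (Section 1.2.3.3), 10 mg daily column.**
- Inputs: n = 45. Bracketed counts are patients at grade 3 or above: rash 1, fatigue 1. The plan enrolls 110 (Protocol Section 4).
- The brackets for rash and fatigue agree with the total column across doses: rash 1; fatigue 1 + 1 + 1 = 3.
- With no grade 4 events, both events were grade 3. One patient could have had both, so the count is at most 1 + 1 = 2.
- Rate: 2/45 = 0.044, or 4.4%.
- Expected here: 0.044 × 110 = 4.9. With the SAP's figure of about 142 enrolled, 0.044 × 142 = 6.3.
- The share of such events that patients tolerate is not in the documents. Letting it run from 0 to 1 gives 0 to 4.9 of 110.

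**The case against.** The strongest reply is that the documents already resolve the clash. Table 3 is called the procedure to follow, Sections 6.1.2 and 6.1.4.3 point the same way, and SAP 3.2 cites only the tables. The disputed sentence nearly repeats the grade 2 row of Table 3, and the sentence after it cites that table, so it reads as a loose lead-in. If tolerability really controlled entry to the tables, most Table 3 rows, which act on grade alone, would lose their stated effect.

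Most of this stands. It shows intent, and it is why the severity is low. A reader might infer that the protocol has no governing rule at grade 3, or that dose reduction there is optional. The documents do not support that: the rule is in Table 3 and is unconditional.

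What the reply does not do is remove the conflict. Intent has to be inferred, and the opening of 6.1.3 can be read the other way, because it ties adjustment to patients who cannot tolerate the schedule and ties the tables to unacceptable toxicity. The SAP is not a dosing instruction for sites.

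**Conclusion.** The 6.1.3 sentence is wrong as written for tolerated grade 3 non-hematological toxicity (hyperlipidemia excepted) and for grade 4. The consequence is a possible misreading at a site, not a missing rule. Severity is low, and neither the PFS analysis nor the sample size depends on the sentence.

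For rash and fatigue the size is about 5 of 110 patients before any tolerated share is applied. This assumes that the phase 1 rate carries over, and it rests on at most two patients. These are examples and not a full count of grade 3 events.

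Two larger readings are tempting and should be resisted:

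- **Using all grade 3 or above events.** Table 1 shows 14 of 45 (31.1%) on 10 mg daily, which would be about 34 of 110. The brackets listed by event in that column sum to 1 (rash) + 3 (stomatitis) + 1 (fatigue) + 1 (nausea) + 1 (infection) = 7. At least 14 − 7 = 7 patients therefore have no identified event type. Section 6.1.4.1 describes grade 3 stomatitis as preventing adequate oral intake, and the one grade 3 infection was pneumonia, so neither is a natural example of a tolerated event. The documents do not support 34 as the number exposed, and no tolerated share can be sourced to scale it.
- **Treating hyperglycemia as a separate gap.** Section 6.1.4.2 says "Grade 3 hyperglycemia has been observed in patients receiving RAD001 therapy" and gives monitoring without a dose action. Such an event still falls in Table 3's grade 3 row, and 6.1.2 sends laboratory abnormalities to that table.

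**What to change.** Replace the two tolerability sentences in 6.1.3 with:

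> Dose is maintained, interrupted, reduced or discontinued by toxicity type and grade as specified in Table 3, Table 4 and the hepatitis reactivation tables, regardless of tolerability; tolerability decides only for grade 2 non-hematological toxicity other than pneumonitis.

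Do not add a clause letting tolerability decide where no action is listed. Table 3 has no grade-specific row for hemoglobin or white cell count, so such a clause would expressly allow full dosing through tolerated grade 3 or 4 anemia or leukopenia. Whether Table 3 should list those toxicities is a separate question.

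The cost is one edit in a protocol amendment and a memo to sites. The analysis does not change.
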